#### **4.4. Exclusion criteria for enrolment**

Deviations from exclusion criteria are not allowed because they can potentially jeopardise the scientific integrity of the study, regulatory acceptability or subject safety. Therefore, adherence to the criteria as specified in the protocol is essential.

The following criteria should be checked at the time of study entry. If ANY exclusion criterion applies, the subject must not be included in the study:

- Child in care.

Please refer to the [glossary of terms](#) for the definition of child in care.

***(Amended 06 May 2015.)***

- Use of any investigational or non-registered product (drug or vaccine) other than the study vaccine during the period starting 30 days before the Day 0 visit, or planned use during the study period.
- Previous vaccination with an investigational EBOV or Marburg vaccine, or previous vaccination with a chimpanzee adenoviral vectored investigational vaccine.
- Known prior EBOV or SUDV disease.
- Travel to country affected by the EBOV epidemic or direct contact with person with EVD within 21 days prior to the Day 0 visit.

- History of any reaction or hypersensitivity (such as anaphylaxis, urticaria [hives], respiratory difficulty, angioedema, or abdominal pain) likely to be exacerbated by any component of the study vaccine.
- Planned administration/ administration of a vaccine not foreseen by the study protocol in the period starting 30 days before and ending 30 days after each vaccination visit.
- Acute or chronic illness determined by medical history, clinical examination and laboratory screening tests including, but not limited to:
  - Clinically significant immunosuppressive or immunodeficient condition (*e.g.*, clinical acquired immune deficiency syndrome [AIDS]).
  - Major congenital defects.
  - Malnutrition (defined as weight for age Z-score less than -3, or other clinical signs of malnutrition).
  - Any clinically significant haematological or biochemical laboratory abnormality (see [APPENDIX C](#) for acceptable limits for eligibility determination).
- Pregnant female.
- *Any condition that in the Investigator's opinion may potentially compromise subject safety or interfere with subject assessment or compliance.*

*(Amended 06 May 2015.)*

## **5. CONDUCT OF THE STUDY**

### **5.1. Regulatory and ethical considerations, including the informed consent process**

The study will be conducted in accordance with all applicable regulatory requirements.

The study will be conducted in accordance with the International Conference on Harmonisation (ICH) Guideline for Good Clinical Practice (GCP), all applicable subject privacy requirements and the guiding principles of the Declaration of Helsinki.

The study has been designed and will be conducted in accordance with the ICH Harmonised Tripartite Guideline for clinical investigation of medicinal products in the paediatric population (ICH E11) and all other applicable ethical guidelines.

GSK Biologicals/ the contracted research organisation (CRO) engaged to conduct the study will obtain favourable opinion/ approval to conduct the study from the appropriate regulatory agency, in accordance with applicable regulatory requirements, prior to a vaccination centre initiating the study in that country.

Conduct of the study includes, but is not limited to, the following:

- Institutional Review Board (IRB)/Independent Ethics Committee (IEC) review and favourable opinion/approval of study protocol and any subsequent amendments.

- Subject's parent(s)/ LAR(s) informed consent and subject informed assent, as appropriate.
- Investigator reporting requirements as stated in the protocol.

GSK/ the CRO will provide full details of the above procedures to the Investigator, either verbally, in writing, or both.

Freely given and written or witnessed/ thumb printed informed consent from each subject's parent(s)/ LAR(s) and subject informed assent, as appropriate, must be obtained prior to participation in the study.

GSK Biologicals/ the CRO will prepare a model informed consent form (ICF) which will embody the ICH GCP and GSK Biologicals required elements. While it is strongly recommended that this model ICF is to be followed as closely as possible, the informed consent requirements given in this document are not intended to pre-empt any local regulations which require additional information to be disclosed for informed consent to be legally effective. Clinical judgement, local regulations and requirements should guide the final structure and content of the local version of the ICF.

In accordance with the ICH Harmonised Tripartite Guidelines for Good Clinical Practice, subjects who can only be enrolled in the study with the consent of their parent(s)/ LAR(s) (*e.g.*, minors), should be informed about the study to the extent compatible with the subject's understanding and, if capable, the subject should sign and personally date a written informed assent form (IAF). It should be assessed whether an assent is required depending of the age of the study population and the local requirements. In this study, written/ thumb printed informed assent should be obtained from all subjects in the oldest age category (13 to 17 year olds) and from younger subjects as per local requirements in addition to the informed consent that is to be signed/ thumb printed by their parent(s)/ LAR(s).

GSK Biologicals strongly recommends that if a subject reaches the age of consent during the study, he/ she will be asked to provide consent at the next study visit (if applicable). This procedure should be applied according to local laws and regulations.

The Investigator has the final responsibility for the final presentation of the ICF and IAF, respecting the mandatory requirements of local regulations. The ICF and IAF generated by the Investigator with the assistance of the sponsor's/ the CRO's representative must be acceptable to GSK Biologicals and be approved (along with the protocol, and any other necessary documentation) by the IRB/ IEC.

## **5.2. Subject identification and randomisation of treatment**

### **5.2.1. Subject identification**

Subject identification numbers will be assigned sequentially to the subjects who have consented to participate in the study. The subject numbers will be assigned as a combination of the centre number and a sequential number.

**5.2.2. Randomisation of treatment****5.2.2.1. Randomisation of supplies**

The ChAd3-EBO-Z vaccine and *Nimenrix* will be numbered sequentially and packed separately.

To allow GSK Biologicals to take advantage of greater rates of recruitment than anticipated at individual centres in this multi-centre study and to thus reduce the overall study recruitment period, an over-packaging of supplies will be prepared.

**5.2.2.2. Treatment allocation to the subject**

The treatment name will be allocated by dose to each subject.

**5.2.2.2.1. Study group and treatment name allocation at Day 0**

The target will be to enrol approximately 600 eligible children who will be randomly assigned to 2 study groups in a (1: 1) ratio (approximately 300 per group and approximately 200 per age stratum).

The enrolment will be performed to ensure equal distribution of the population across the 3 age strata (1 to 5 years, 6 to 12 years, and 13 to 17 years of age). Therefore the expected distribution of subjects is as shown in Table 4.

**Table 4 Number of subjects required for enrolment**

Age Stratum	Group	N
1 to 5 years	EBO-Z/ MENACWY-TT	100
	MENACWY-TT/ EBO-Z	100
6 to 12 years	EBO-Z/ MENACWY-TT	100
	MENACWY-TT/ EBO-Z	100
13 to 17 years	EBO-Z/ MENACWY-TT	100
	MENACWY-TT/ EBO-Z	100

N = number of subjects to be enrolled

Allocation of the subject to a study group at the vaccination centre will be performed using a central Interactive Web Response System (IWRS). In addition to the IWRS, an Interactive Voice Response System (IVRS) will be available in case of possible connectivity issues with the IWRS. Within each age stratum (1 to 5 years, 6 to 12 years, and 13 to 17 years of age), the randomisation algorithm will use a minimisation procedure accounting for gender and centre. The minimisation is a dynamic allocation method that will ensure that, within each age stratum, there is a good balance between groups in the number of subjects by gender and centre. Both minimisation factors will have equal weight in the minimisation algorithm.

After obtaining the signed/ thumb printed and dated ICF from the subject's parent(s)/ LAR(s) and signed/ thumb printed and dated IAF from the subject (if applicable) and having checked the eligibility of the subject, the site staff in charge of the vaccine administration will access IWRS/ IVRS. Upon providing the subject's age (1 to 5 years *versus* 6 to 12 years *versus* 13 to 17 years of age), gender, centre and the subject

identification number, the randomisation system will determine the study group and will provide the treatment name to be administered. Access to the IVRS/ IWRS ***unblinded treatment information*** will be limited to unblinded site staff. (*Amended 06 May 2015.*)

After vaccine administration, the treatment number of the vaccine administered (indicated on the label) should be recorded in IWRS/ IVRS, and for drug supply management purposes, by the unblinded study staff preparing and administering the vaccine. The applicable screen will only be available for unblinded staff in order to maintain the study blind.

When IWRS is not available, please refer to the relevant user guide for instructions for the use of the IVRS.

Note that as soon as the target number of 200 subjects in a specific age group has been reached, the enrolment will be frozen for this age group.

#### **5.2.2.2. Treatment name allocation at Month 6**

At Month 6, the study staff in charge of the vaccine administration will access IWRS/ IVRS, provide the subject identification number, and the system will provide a treatment name consistent with the allocated study group.

The number of the administered treatment should be recorded in the IWRS/IVRS by study staff preparing the vaccine.

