### **1.3. Benefit : Risk assessment**

All subjects in the study will receive a single dose of the investigational ChAd3-EBO-Z vaccine (either at Day 0 or at Month 6 of the study) and a single dose of *Nimenrix* (at Day 0 or at Month 6 of the study).

For general information on the risks and benefits of the investigational ChAd3-EBO-Z vaccine and *Nimenrix*, please refer to the current Investigator Brochure (IB), Periodic Safety Report Information (PSRI) and to the approved summary of product characteristics (SmPC)/ Prescribing Information/ package insert, as applicable.

The following section outlines the risk assessment and mitigation strategy for this study protocol.

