**Table 2 Treatments foreseen in the study**

Treatment name	Vaccine/Product name	Study Groups	
		EBO-Z/ MENACWY-TT	MENACWY-TT/ EBO-Z
ChAd3-EBO-Z	ChAd3-EBO-Z	x (Day 0)	x (Month 6)
Nimenrix	MenACWY-TT NaCl	x (Month 6)	x (Day 0)

**ChAd3-EBO-Z** = investigational recombinant chimpanzee adenovirus type 3-vectored Ebola virus Zaire (EBOV) vaccine; **NaCl** = sodium chloride

- **Control:** Active control (*Nimenrix*).
- **Vaccination schedule:** All subjects will receive 2 vaccinations, 1 at the Day 0 visit and 1 at the Month 6 visit. All subjects will receive 1 dose of the investigational ChAd3-EBO Z vaccine and 1 dose of *Nimenrix*:
  - Subjects in Group EBO-Z/ MENACWY-TT will receive the investigational ChAd3-EBO-Z vaccine at the Day 0 visit and *Nimenrix* at the Month 6 visit.
  - Subjects in Group MENACWY-TT/ EBO-Z will receive *Nimenrix* at the Day 0 visit and the investigational ChAd3-EBO-Z vaccine at the Month 6 visit.

- **Treatment allocation:** Subjects will be randomised (1:1) at Day 0. In order to ensure equal distribution of the population, enrolment will be stratified by age so that an equal number of children are enrolled in each age stratum (1 to 5 years, 6 to 12 years, and 13 to 17 years of age). In addition, the randomisation will use a minimisation procedure accounting for gender and centre.
- **Staggered vaccination:** Vaccination at Day 0 will be done in a staggered manner, starting with vaccination of the children in the oldest age stratum (13 to 17 years of age). In order to proceed to vaccination of the subjects in the younger age stratum (6 to 12 years of age), possibly with a lower vaccine dose, a favourable outcome of the IDMC review of safety data up to at least 7 days after vaccination from at least 50 subjects (25/ group) in the oldest age stratum needs to be obtained. The same will be done for moving from the 6 to 12 years of age stratum to vaccination of the youngest children (1 to 5 years of age). Refer to [Section 9.10](#) for more information.
- **Blinding:**
  - **Observer-blind** from study start until the interim analysis that will be conducted when safety, reactogenicity and immunogenicity (including at least anti-GP EBOV data at Day 30) data is available from all subjects up to 30 days after vaccination at Day 0 (refer to [Section 11.11.1](#) for more information on this interim analysis).
  - **Single-blind** as of the interim analysis *at Day 30. (Amended 06 May 2015.)*
- **Sampling schedule:**

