**CONFIDENTIAL**

202090 (EBOLA Z CHAD3-004)  
Protocol Amendment 2 Final

Type of contact	Visit	Visit	Visit	Visit	Visit	Contact *	Visit	Visit	Visit	Contact *	Visit
Timepoint	Screening 	Day 0 	Day 3	Day 6	Day 30	Month 3	Month 6	Month 6 + 6 days	Month 6 + 30 days	Month 9	Month 12
Record concomitant medications/ products/ vaccinations 		•	•	•	•	•	•	•	•	•	•
Screening Conclusion	•										
Study Conclusion											•

~ = approximately; **AE** = adverse event; **CMI** = cell-mediated immunity; **CRO** = Contract research organisation; **EVD** = Ebola virus disease; **GSK** = GlaxoSmithKline; **RDT** = *Rapid*

**Diagnostic Test**; **SAE** = serious adverse event

• is used to indicate a study procedure that requires documentation in eSource.

○ is used to indicate a study procedure that does not require automatic transfer of the study data fields from the source database into the study database at the CRO.

\* Home visit by field worker or phone call.

 The Screening visit and the Day 0 visit may take place on the same day (allowed interval 0 to 30 days).

 Refer to [Section 5.6.6](#) for the specific assessments included in the physical examination.

 Only if Visit 1 and Screening take place on a different day.

 Only for women of childbearing potential.

 Only if Visit 1 takes place more than 1 week after the Screening Visit.

 Treatment name allocation with randomisation at Day 0; treatment name allocation without randomisation at Month 6.

 Only for subjects in the sub-cohort for cell-mediated immunity (CMI).

 From Screening to Day 0, only those SAEs that are considered related to study participation or to concurrent use of GlaxoSmithKline (GSK) medication/ vaccine need to be recorded.

 Concomitant medications/ products/ vaccinations as described in [Section 6.7.1](#) and [6.7.2](#) need to be recorded in eSource.

 Only for subjects in the oldest age stratum (13 to 17 year olds) and younger subjects as per local requirements.

 **Subjects diagnosed with Malaria at Screening must receive antimalarial treatment according to local/ national standards (e.g., a 3-day treatment course of artemisinin-based combination therapy), during the Screening period.**

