### 5.3. TOTAL VACCINATED COHORT (TVC)

The Total Vaccinated Cohort (TVC) is defined as all subjects included in the Total Randomised Cohort who received at least one vaccination. The TVC is defined separately for safety and immunogenicity analyses as described below:

- Safety Analysis:

---

Document: CHAD3-004-EBO-Z\_Interim\_Final\_SAP\_v2\_0  
Author: PPD Version Number: 2.0 Version Date: 14JUN2017

Template No: CS\_TP\_BS016 – Revision 3  
Effective Date: 01May2012

Reference: CS\_WI\_BS005

- o A subject is to be programmatically included in the TVC if the subject has at least one date of vaccination available in the database.
  - o Labelled as 'Total Vaccinated Cohort' in relevant TLF shells.
- Immunogenicity Analysis:
  - o Immunogenicity analysis based on the TVC will include all vaccinated subjects for whom immunogenicity results are available, however, due to the fact that only subjects with data available are to be included per time point for the immunogenicity analysis, there will be no additional elimination required. The TVC for safety and immunogenicity analyses are defined as the same cohort of subjects.

Subjects who received a different treatment to that allocated are to be analysed as described below:

- Analyse subject according to the treatment received at Day 0 (first vaccination).

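### For a child given the other study vaccine in error at Day 0, the Month 6 rule as written yields two ChAd3-EBO-Z doses or none, and the SAP's pooled tables then take the Month 6 vaccine from the group label

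*Protocol*

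**What the plan says.** **Protocol**

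- Treatment name allocation at Month 6 (5.2.2.2.2 in the table of contents): staff "provide the subject identification number, and the system will provide a treatment name", and that name is tied to the allocated group: "the system will provide a treatment name consistent with the allocated study group". A footnote to Table 5 describes this as "treatment name allocation without randomisation at Month 6".
- Section 5.2.2.2.1: after the Day 0 injection, "the treatment number of the vaccine administered (indicated on the label) should be recorded in IWRS/ IVRS, and for drug supply management purposes".
- Section 1.3: "All subjects in the study will receive a single dose of the investigational ChAd3-EBO-Z vaccine", at Day 0 or at Month 6. The vaccination schedule in Section 3 says "All subjects will receive 1 dose of the investigational ChAd3-EBO Z vaccine and 1 dose of" Nimenrix.
- Section 6.6 lists three absolute contraindications at Month 6: anaphylaxis, immunosuppression or immunodeficiency, and pregnancy. The vaccine already received is not among them. Earlier vaccination with an Ebola or chimpanzee-adenovirus vaccine is an exclusion criterion (4.4), checked at study entry.
- Section 11.5.1: the total vaccinated cohort (TVC) is analysed by the treatment actually administered.

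**SAP version 2.0**

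- Section 5.3: "Subjects who received a different treatment to that allocated are to be analysed as described below". The single instruction that follows is to use the treatment received at Day 0. Month 6 is not mentioned.
- Section 6.3.1 (Table 2) and Sections 15.1.2, 15.2.2 and 15.4 build the pooled post-ChAd3-EBO-Z data by group: from Day 0 for EBO-Z/MENACWY-TT, from Month 6 for MENACWY-TT/EBO-Z.
- Section 13 imports the vaccine actually administered (EBO-Z or Nimenrix).

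**The concern.** The SAP provides for children who receive a vaccine other than the one allocated, but the Month 6 allocation rule does not. Taken literally, that rule turns a Day 0 swap into a repeat of the same vaccine: an unplanned second dose of an investigational vector, or two control doses and no ChAd3-EBO-Z. Either outcome departs from the one-dose-of-each statement and from the primary objective, which concerns a single ChAd3-EBO-Z dose.

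The analysis rules add a second problem. SAP 5.3 moves the child to the group that matches the Day 0 vaccine. The pooled tables then assume that the group label also fixes the Month 6 vaccine. After a swap it does not, so a window can be attributed to the wrong vaccine, contrary to Protocol 11.5.1.

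**Working it through.** **Step 1: the plan's own figure.** The stated exposure is one dose of each vaccine per child. Applying the Month 6 rule and then SAP 5.3 and 6.3.1 to each combination of randomised group and Day 0 vaccine gives:

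| Randomised group | Day 0 given | Month 6 issued | ChAd3-EBO-Z / Nimenrix doses | Group under SAP 5.3 | Window pooled as post-ChAd3-EBO-Z | Vaccine actually given there |
|---|---|---|---|---|---|---|
| EBO-Z/MENACWY-TT | ChAd3-EBO-Z | Nimenrix | 1 / 1 | EBO-Z/MENACWY-TT | Day 0 | ChAd3-EBO-Z |
| MENACWY-TT/EBO-Z | Nimenrix | ChAd3-EBO-Z | 1 / 1 | MENACWY-TT/EBO-Z | Month 6 | ChAd3-EBO-Z |
| EBO-Z/MENACWY-TT | Nimenrix (error) | Nimenrix | 0 / 2 | MENACWY-TT/EBO-Z | Month 6 | **Nimenrix** |
| MENACWY-TT/EBO-Z | ChAd3-EBO-Z (error) | ChAd3-EBO-Z | 2 / 0 | EBO-Z/MENACWY-TT | Day 0 | ChAd3-EBO-Z (second dose falls outside the pool) |

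The first two rows reproduce the stated figure. The last two do not.

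**Step 2: where the data go.**

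- *Zero-dose child.* A Nimenrix window enters the pooled ChAd3-EBO-Z safety tables, which use the TVC without any condition.
- *Two-dose child.* The Day 0 window is pooled correctly. Events after the second dose are outside the pooled incidence tables, and also outside the standard ones, which are restricted to the Day 0 window. Laboratory values at Month 6 + 6 days and later appear by visit under a label that implies Nimenrix at Month 6.
- *Antibody persistence.* Month 6 + 30 days and Month 12 values after a second dose can appear only in the by-group TVC tables. Those are produced only if at least 5% of a group is excluded from the according-to-protocol (ATP) cohort: 0.05 × 300 = 15 children.

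**Step 3: how many children.** The documents give no error rate, so the rates r below are assumptions. Expected number = 600r; probability of at least one = 1 − (1 − r)^600.

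| Assumed r | Expected children | P(at least one) |
|---|---|---|
| 0.1% | 0.6 | 0.45 |
| 0.2% | 1.2 | 0.70 |
| 0.5% | 3 | 0.95 |
| 1% | 6 | 0.998 |
| 2% | 12 | about 1.0 |

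**Step 4: effect on results.** One zero-dose child changes a pooled incidence by at most 1/600 = 0.17 percentage points overall, or 1/200 = 0.5 points in an age stratum. If all of 6 errors were of this kind, the limit overall would be 6/600 = 1.0 point. For persistence, suppose a second dose raised one child's concentration tenfold (assumed): the geometric mean would shift by 10^(1/300) = 1.008, or 0.8%, in a group of 300, and by 10^(1/100) = 1.023, or 2.3%, in a stratum of 100.

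**The case against.** The best defence is that the Protocol is consistent for every child vaccinated as allocated, and that a plan need not script the aftermath of every deviation. Much of this stands.

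- *Frequency.* The error must be receipt of the other study vaccine; a wrong vial of the right vaccine does not produce the result. The two products are packed separately (5.2.2.1) and look different (Table 14: a liquid in a vial against a powder with a prefilled diluent syringe), and the system supplies the treatment name. A reader might infer from SAP 5.3 that swaps are expected. That section is a contingency rule and predicts no rate.
- *Unseen checks.* A reader might infer that the system disregards the Day 0 record. The documents do not say so; they are silent. The IWRS holds the Day 0 treatment number, and a comparison may sit in its specification, the Pharmacy Manual or the site vaccine management plan.
- *Main antibody results.* A reader might infer that the persistence results are contaminated. The ATP cohort is primary for immunogenicity, and SAP 5.4 says its members received no treatment other than that allocated. The listed criterion (at least one dose as randomised) is looser than that statement, but the intended exclusion is clear.
- *Existing safeguards.* Vaccine administration and protocol violations are listed, and SAEs are tabulated by most recent dose.

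The pooling rule is not answered by any of this. Its lead-in speaks of events following ChAd3-EBO-Z, but its operative lines select by group and visit. Once SAP 5.3 has relabelled a child by the Day 0 vaccine, those lines give the wrong window for a zero-dose child.

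**Conclusion.** The concern holds, conditionally. After a Day 0 swap, the Month 6 rule read literally cannot deliver one dose of each vaccine, and no supplied section states a check that would intervene. The SAP's rule for mis-dosed children and its rule for pooling do not fit together: a Nimenrix window can be counted as ChAd3-EBO-Z, and data after a second ChAd3-EBO-Z dose can be presented as following Nimenrix.

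This is not a general contradiction between the schedule and the allocation rule, because they diverge only after an administration error. The numerical effect on a descriptive study is small under every rate assumed here. The reason to act is that each affected child would have an exposure the Protocol does not intend, and that the analysis side can be corrected with data already planned for import. The conclusion rests on a literal reading of the Month 6 rule and on assumed error rates, and it would weaken if a check is documented elsewhere.

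**What to change.** **Protocol.** Reconcile Section 1.3, the vaccination schedule in Section 3, the Month 6 allocation section and Section 6.6 for a child given the other study vaccine at Day 0. Which vaccine, if any, such a child receives at Month 6 is a clinical decision for the sponsor; none is proposed here. If a comparison with the Day 0 treatment number already exists in another document, cite it.

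**SAP 5.3 and 6.3.1**, with matching wording in 15.1.2, 15.2.2 and 15.4:

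- Define each post-ChAd3-EBO-Z window by the vaccine actually administered at that visit, using the variable imported under Section 13.
- Exclude from single-dose summaries any data collected after a second dose of the same study vaccine.
- List the children concerned.

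The cost is a short Protocol clarification and a few SAP sentences with matching programming. No new data are needed.
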